C _{ss}	average plasma concentration at steady-state
CRO	contract research organization
CSR	Clinical Study Report
CTCAE	Common Terminology Criteria for Adverse Events
DFS	disease-free survival
DMC	Data Monitoring Committee
ECG	electrocardiogram
ECOG	Eastern Cooperative Oncology Group
eCRF	electronic case report form
EDC	electronic data capture
EORTC	European Organization for Research and Treatment of Cancer
EOS	end of study
EQ-5D	EuroQOL five dimensions questionnaire
FGFR3	fibroblast growth factor receptor 3
HR	hazard ratio
ICH	International Council for Harmonization
ITT	intent-to-treat
K-M	Kaplan Meier
LVEF	left ventricular ejection fraction
MFS	metastasis-free survival
MedDRA	Medical Dictionary for Regulatory Activities
MIBC	muscle invasive bladder cancer
NMIBC	non-muscle invasive bladder cancer
OS	overall survival
PD-L1	programmed death-ligand 1
PK	pharmacokinetics
PR	partial response
QLQ	quality of life questionnaire
QOL	quality of life
QTcF	QTc corrected by Fridericia's formula
R _{acc}	accumulation ratio calculated as C _{min} steady-state/C _{min}
SAE	serious adverse event
SAP	Statistical Analysis Plan
SOC	system organ class
UBC	urothelial carcinoma of the bladder

UTUC

upper tract urothelial carcinoma

1 INTRODUCTION

The purpose of this statistical analysis plan (SAP) is to provide details of the statistical analyses that have been outlined within the protocol for study QBGJ398-302 dated 19 May 2021. Consequent to the business decision by Helsinn Healthcare SA (HCC) on 5 October 2022 to stop the distribution of TRUSELTIQ and to withdraw new drug and marketing authorization applications worldwide, the further development of infigratinib in oncology outside of China was terminated which subsequently led to the closure of this study. The decision was not made based on any efficacy or safety concerns. With the limited number of patients randomized, the number of disease-free survival events required to assess the efficacy objectives was not achieved to the futility of the study.

The scope of this plan includes the early terminated study analysis. The analyses detailed within this plan will describe the efficacy and safety (primary and secondary study objectives) observed in the limited patients enrolled of adjuvant treatment of infigratinib for subjects with invasive urothelial carcinoma with susceptible fibroblast growth factor receptor (FGFR)3 genetic alterations (mutations, and gene fusions or translocations [ie, rearrangements]; hereafter referred to collectively as “FGFR3 alterations”).

The PK of infigratinib has been well described as part of the conditional approvals granted in the treatment of adults with previously treated, unresectable locally advanced or metastatic cholangiocarcinoma with FGFR2 fusion or other rearrangement as detected by an FDA-approved test. Given the study and development termination, neither the PK nor the other exploratory endpoints (QoL and cfDNA) will be described.

No interim analysis and sample size adjustments were conducted given the timing of the early termination of the study.

2 OBJECTIVES

2.1 Primary Objective

The primary objective is to determine if treatment with infigratinib improves centrally reviewed disease-free survival (DFS) compared with placebo treatment in subjects with invasive urothelial carcinoma with susceptible FGFR3 alterations after nephro-ureterectomy, distal ureterectomy, or cystectomy.

2.2 Secondary Objectives

The secondary objectives include:

- To compare DFS including intraluminal low risk recurrence in subjects treated with infigratinib vs placebo.
- To compare metastasis-free survival (MFS) of subjects treated with infigratinib vs placebo.
- To compare the overall survival (OS) in subjects treated with infigratinib vs placebo.

- To compare the investigator-reviewed disease-free survival (DFS) of subjects treated with infigratinib vs placebo.
- To characterize the safety and tolerability of infigratinib when administered as postoperative adjuvant monotherapy.

2.3 Exploratory Objectives

The exploratory objectives are not conducted due to the abbreviated Clinical Study Report (CSR).

3 STUDY DESIGN

3.1 Overall Study Design

This is a Phase 3 multicenter, double-blind, randomized, placebo-controlled study to evaluate the efficacy of infigratinib in approximately 218 adult subjects with invasive urothelial carcinoma with susceptible FGFR3 alterations who are within 120 days following nephron-ureterectomy, distal ureterectomy, or cystectomy and ineligible for cisplatin-based adjuvant chemotherapy or with residual disease after neoadjuvant therapy. The sample size can be potentially increased up to a total of 328 subjects based on interim analysis result using an adaptive design promising zone approach ([Mehta and Pocock 2011](#)). Subjects with invasive urothelial carcinoma include subjects with invasive upper tract urothelial carcinoma (UTUC) and urothelial carcinoma of the bladder (UBC). The interim analysis is actually not conducted because the study is early terminated by sponsor.

Subjects will be randomized 1:1 to receive oral infigratinib or placebo administered once daily for the first 3 weeks (21 days) of each 28-day cycle for 52 weeks or until local/regional invasive or metastatic recurrence, unacceptable toxicity, withdrawal of informed consent, or death. Subjects will be evaluated for tumor recurrence radiographically every 3 months for the first 24 months, and annually thereafter or until recurrence by blinded independent central review (BICR) (local/regional invasive or metastatic) or metastatic recurrence by investigator assessment, whichever comes later. For subjects with UTUC (ie, subjects with a bladder), cystoscopy and urine cytology will be performed at 3, 6, 9, and 12 months, then every 6 months up to 24 months, and then annually until subjects experience recurrence by BICR (local/regional invasive or metastatic) or metastatic recurrence by investigator assessment, whichever is later. After that time, subjects will be followed for survival status and use of anticancer therapy approximately every 6 months (via phone or office visit) up to 1 year, then annually thereafter for 1 year after the final DFS event goal is reached (ie, End of Study [EOS]).

3.2 Stratification Factors

Subjects will be stratified according to lymph node involvement (yes vs no), prior neoadjuvant chemotherapy (yes vs no), AJCC Stage ((y)pT2 vs (y)pT3-4), and disease (UTUC vs UBC). Approximately 218 subjects will be randomized across approximately 100 centers worldwide. After interim analysis, the sample size may be increased up to a total of 328 subjects.

3.3 Sample Size Considerations

Approximately 218 subjects will be initially randomized in this study in a double-blind fashion. The sample size can be potentially increased up to a total of 328 subjects based on interim analysis result using an adaptive design promising zone approach ([Mehta and Pocock 2011](#)). The study will start with a group sequential design with one interim analysis at approximately 35 centrally reviewed DFS events (50% of the initial event goal). A Haybittle-Peto boundary will be used for the efficacy boundary with a fixed one-sided alpha (α) of 0.00005 spent at the interim analysis for DFS, and the rest of the alpha (one-sided α 0.025) spent at the primary DFS analysis. Though an efficacy boundary is specified for the interim DFS analysis, the trial will not stop at the interim analysis if the efficacy boundary is crossed. A Lan DeMets alpha spending function approximating O'Brien-Fleming boundary will be used for non-binding futility boundary. Assuming disease will recur in 46% of subjects in the first 2 years and a 5% yearly recurrence rate in the third year and beyond for the placebo group, the required sample size with initial group sequential design is approximately 218 subjects to reach 70 centrally reviewed DFS events in 4 years. This is assuming with three-year uniform enrollment, one-year follow-up, 10% yearly drop-out rate and a hazard ratio (HR) of 0.5 (2-year DFS 73% in infigratinib arm vs 54% in placebo arm). The sample size will provide approximately 80% power to detect a difference in DFS assuming an HR of 0.5 comparing infigratinib vs placebo, based on a log-rank test controlling type I error at one-sided 0.025.

At the interim analysis, the study uses an adaptive design promising zone approach ([Mehta and Pocock 2011](#)) to adjust sample size and event as needed. The details of the sample size adaptation method will be pre-specified in the adaptation plan. If no sample size adaption is needed at the interim analysis, the study is projected to reach the planned number of centrally reviewed DFS events (70) 4 years from the randomization of the first subject. If a sample size increase is deemed necessary based on the interim result and the promising zone approach, the sample size/centrally reviewed event goal will be increased by maximum of 50% (328/105). If sample size is increased and event goal is adjusted, then the subsequent analyses will be adjusted accordingly timewise when the adjusted event goal is reached. The boundary to test centrally reviewed DFS when the adjusted event goal is reached will be based on the original boundaries of the initial group sequential design.

4 STUDY ENDPOINTS AND COVARIATES

4.1 Endpoints

The primary endpoint is:

- Centrally reviewed DFS, from date of randomization to local/regional invasive or metastatic recurrence or death due to any cause, whichever occurs earlier.

The secondary endpoints are:

- Investigator reviewed DFS including intraluminal low-risk recurrence, from date of randomization to any recurrence or death due to any cause, whichever occurs earlier.

- Investigator reviewed MFS, from date of randomization to metastatic recurrence or death due to any cause, whichever occurs earlier.
- OS (from randomization to death).
- Investigator reviewed DFS, from date of randomization to local/regional invasive or metastatic recurrence or death due to any cause, whichever occurs earlier.
- Type, frequency, and severity of adverse events and serious adverse events, laboratory abnormalities, and other safety findings.

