4 OBJECTIVES AND ENDPOINTS

[Table 4](#) presents the study objectives and endpoints defined in Section [10](#).

Table 4: Objectives and Endpoints

Objectives	Endpoints
Primary: To determine if treatment with infigratinib improves centrally reviewed disease-free survival (DFS) compared with placebo treatment in subjects with invasive urothelial carcinoma with susceptible FGFR3 alterations after nephroureterectomy, distal ureterectomy, or cystectomy	Centrally reviewed DFS, from date of randomization to local/regional or contralateral invasive or metastatic recurrence, or death due to any cause, whichever occurs earlier
Secondary: To compare DFS including intraluminal low-risk (noninvasive, low-grade, or high-grade) recurrence in subjects treated with infigratinib vs placebo To compare metastasis-free survival (MFS) of subjects treated with infigratinib vs placebo To compare OS in subjects treated with infigratinib vs placebo To compare investigator-reviewed DFS in subjects treated with infigratinib vs placebo To characterize the safety and tolerability of infigratinib when administered as postoperative adjuvant monotherapy	Investigator-reviewed DFS including intraluminal low-risk (noninvasive, low-grade, or high-grade) recurrence, from date of randomization to any recurrence or death due to any cause, whichever occurs earlier Investigator-reviewed MFS, from date of randomization to metastatic recurrence or death due to any cause, whichever occurs earlier OS (from date of randomization to death) Investigator-reviewed DFS, from date of randomization to local/regional or contralateral invasive or metastatic recurrence, or death due to any cause, whichever occurs earlier Type, frequency, and severity of adverse events and serious adverse events, laboratory abnormalities, and other safety findings

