If a subject discontinues treatment prematurely for reasons other than local/regional or contralateral invasive or metastatic recurrence, CT/MRI scans (chest, abdomen, and pelvis), cystoscopy (for subjects with a bladder), and urine cytology should continue to be taken at the intervals outlined in [Table 2](#). For subjects started on a non-study related anticancer therapy after discontinuing from study treatment, imaging assessment of disease status should continue until metastatic recurrence by BICR or metastatic recurrence by investigator assessment if local/regional or contralateral invasive recurrence by BICR has already occurred.

For this study, definitions of recurrence are as follows:

- Local/regional or contralateral invasive recurrence: recurrence of the original diagnosis of invasive urothelial carcinoma (within the urinary tract, renal or ureter bed, urinary soft tissue or locoregional lymph nodes). This does not include local/regional recurrence of noninvasive, or low-grade, or high grade UTUC or NMIBC.
- Metastatic recurrence: Recurrence at any site or lymph node other than the urinary tract or local region of primary tumor.
- Intraluminal low-risk recurrence: Any local/regional or contralateral recurrence of noninvasive, low-grade, or high-grade UTUC or NMIBC.

These determinations will be recorded in the eCRF.

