11.3.3 Efficacy Analyses

The primary objective of the study is to compare the centrally reviewed DFS of subjects with invasive urothelial cancer with susceptible FGFR3 alterations treated with infigratinib vs placebo following nephroureterectomy, distal ureterectomy, or cystectomy.

The primary endpoint is centrally reviewed DFS, from date of randomization to local/regional or contralateral invasive or metastatic recurrence (according to central review) or death due to any

cause, whichever occurs earlier. Criteria for recurrence are specified in Section 10.1. For subjects without a bladder who are alive and without recurrence (local/regional or contralateral invasive or metastatic) by BICR, DFS will be censored at the last radiology assessment. For subjects with a bladder who are alive and without recurrence, DFS will be censored at the last radiology assessment if the previous cystoscopy result within 6 months is negative for muscle invasive disease, otherwise DFS will be censored at the last complete recurrence assessment. Subjects who have no disease assessments after baseline or no death recorded will be censored on the randomization date.

Investigator-reviewed DFS including intraluminal low-risk (noninvasive, low-grade, or high-grade) recurrence is defined as the time from randomization to any recurrence as determined by the investigator, or death due to any cause, whichever occurs earlier. For subjects without documented recurrence and who are still alive, they will be censored at the last complete disease assessment (or, if no complete disease assessments are performed after the baseline visit or no death recorded, at the time of randomization day).

Investigator-reviewed MFS is defined as the time from randomization to any metastatic recurrence as determined by the investigator or death due to any cause, whichever occurs earlier. For subjects without documented metastatic recurrence and who are still alive, they will be censored at the last radiology assessment (or, if no radiology assessments are performed after the baseline visit or no death recorded, at the time of randomization day).

OS is defined as date of randomization to death. For subjects without documented death, they will be censored at the last known to be alive date.

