Disease-free survival time is calculated as the number of months from randomization to the date of local/regional invasive or metastatic recurrence or death due to any cause (referred as DFS event) ((date of DFS event - date of randomization + 1)/ (365.25/12)). Subjects without recurrence (local/regional invasive or metastatic) or death will be censored at the last radiology assessment if previous cystoscopy result within 6 months is negative for muscle invasive disease, otherwise, DFS will be censored at the last complete recurrence assessment. Subjects who have no disease assessments after baseline will be censored on the randomization date. The primary DFS endpoint will be based on the central review (BICR), while for the secondary endpoint, the investigator reviewed DFS will be based on investigator review.

DFS including intraluminal low risk recurrence

The investigator reviewed DFS including intraluminal low risk recurrence is defined as the time from randomization to any recurrence as determined by investigator, or death due to any cause, whichever occurs earlier. For subjects without documented recurrence and are still alive, they will be censored at the last complete disease assessment (or, if no disease assessments are performed after the baseline visit or no death has been recorded, at the time of randomization).

Relative dose intensity

The relative dose intensity is defined as cumulative actual dose a subject have received divided by the planned cumulative dose. For example, a subject takes study drug from Day 1 to Day 21 at 125 mg/day; then from Day 29 to Day 30 at 100 mg/day, and end treatment afterward. The cumulative actual dose $=(21*125)+(100*2)=2825$ mg; the planned cumulative dose $=(21*125)+(125*2)=2875$ mg. The relative dose intensity $= 2825/2875=98.3\%$.

Study Day 1

Study Day 1 is defined as the day of the first administration of study treatment after randomization.

Treatment Duration

Treatment duration is defined as last dose date – first dose date +1.

On Treatment Period

On treatment period is defined as first administration of study treatment through 30 days after the last administration of study treatment inclusively.

Treatment-emergent Adverse Event

A treatment-emergent adverse event is defined as an adverse event that occurs on or after the first administration of study treatment and within 30 days after the last administration of study treatment.

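### The SAP's DFS event and censoring rules leave out contralateral invasive recurrence, which the protocol counts in the same endpoints

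*SAP*

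**What the plan says.** SAP Section 1 states that the plan details the "statistical analyses that have been outlined within the protocol for study QBGJ398-302 dated 19 May 2021". That is the current protocol version.

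SAP Section 4.1 gives the primary endpoint as "Centrally reviewed DFS, from date of randomization to local/regional invasive or metastatic recurrence or death due to any cause, whichever occurs earlier". It uses the same recurrence list for the secondary endpoint of investigator-reviewed DFS. SAP Section 6 derives the event date from "local/regional invasive or metastatic recurrence or death due to any cause (referred as DFS event" and then says: "Subjects without recurrence (local/regional invasive or metastatic) or death will be censored at the last radiology assessment", subject to a condition on cystoscopy. Section 6 applies this one derivation to both the central and the investigator version.

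Protocol Section 4 (Table 4) gives the primary endpoint as "Centrally reviewed DFS, from date of randomization to local/regional or contralateral invasive or metastatic recurrence, or death due to any cause, whichever occurs earlier", with the same list for investigator-reviewed DFS. Protocol Section 11.3.3 repeats the definition. In the censoring sentence for subjects without a bladder it reads: "without recurrence (local/regional or contralateral invasive or metastatic) by BICR, DFS will be censored at the last radiology assessment". The next sentence, for subjects with a bladder, refers to recurrence without repeating the list.

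**The concern.** The two documents define the same two endpoints with different event lists, and the SAP neither announces nor explains a change. The analysis would be programmed from the SAP, and the SAP list is the shorter one.

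At stake is what the reported primary endpoint means. UBC was capped at 15% of the population, so the trial was planned as at least 85% UTUC (100% − 15%). In upper tract disease an invasive recurrence on the opposite side is a recognised possibility, and the protocol names it in the endpoint, in the follow-up rules and among the reasons for ending study drug. If it is not an event, the SAP's descriptive DFS curve is not the protocol's DFS curve, although it carries the same name.

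**Working it through.** **Design figure.** The SAP's 70-event goal was checked first. At 70 events and HR 0.5, Freedman's formula gives power Φ(√70 × 0.5/1.5 − 1.960) = Φ(0.829) = 79.6%, matching the stated 80%. Expected events at 4 years with 218 subjects come to 69.7 to 70.0 under the stated accrual, dropout and recurrence assumptions. None of this depends on the present point, which is a comparison of definitions.

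**Step 1: compare the event lists.**

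| Item | Protocol | SAP |
|---|---|---|
| Centrally reviewed DFS, definition | contralateral included (4, 11.3.3) | omitted (4.1) |
| Investigator-reviewed DFS, definition | contralateral included (4) | omitted (4.1) |
| DFS event derivation | follows the definition | omitted (6) |
| DFS censoring | contralateral named (11.3.3) | omitted (6) |

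The term is missing from 4 of 4 SAP sentences, and it occurs nowhere in the SAP text available for review.

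**Step 2: check whether another SAP category recovers the event.** Protocol Section 10.1 has three recurrence categories. The first is the combined one: "Local/regional or contralateral invasive recurrence: recurrence of the original diagnosis of invasive urothelial carcinoma", which covers the urinary tract among other sites. The second is "Metastatic recurrence: Recurrence at any site or lymph node other than the urinary tract or local region of primary tumor". The third is intraluminal low-risk recurrence. A contralateral upper tract invasive recurrence lies in the urinary tract, so it is not metastatic, and it is invasive, so it is not low-risk. If the SAP's phrase does not cover it, nothing else in the SAP's DFS event does.

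**Step 3: follow one subject.** Let t_c be the date of a BICR contralateral invasive recurrence, t_m the date of a later metastasis or death, and t_L the last qualifying assessment.

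- Protocol: event at t_c.
- SAP read literally, no later event: censored at t_L.
- SAP read literally, later event: event at t_m.

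Under Protocol Section 5.1, scans continue after such a recurrence until metastatic recurrence, so t_L can fall after t_c. If it does, the event at t_c is removed and the subject stays at risk longer. With n at risk and this the only event at t_c, the Kaplan-Meier factor there changes from 1 − 1/n to 1, a relative rise of n/(n − 1), and later factors up to t_L are no smaller. If the event moves to t_m instead, the curve is too high between t_c and t_m.

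**Step 4: check consistency within the SAP outputs.** DFS including intraluminal low-risk recurrence counts any recurrence found by the investigator. A contralateral invasive recurrence would be an event there but not in investigator-reviewed DFS. The two endpoints should differ only by low-risk recurrences; as written they could also differ by an invasive one. Separately, BICR contralateral recurrence is a listed reason for ending study drug (Protocol 8.1.1) and SAP 8.3 tabulates those reasons, so a subject could be listed there with recurrence and have no DFS event at that date.

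**Step 5: size.** The documents give no rate of contralateral invasive recurrence and no event count for the terminated trial, so no number of lost events can be computed.

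**The case against.** The strongest reply is that the SAP wording is shorthand. Protocol 10.1 holds local/regional and contralateral invasive recurrence in one category, Table 8 has no separate contralateral row, and the SAP defines no recurrence categories of its own. A programmer who turned to the protocol would find only the combined category and would count the event. Other SAP text also trails the protocol: Section 3.1 omits subjects who refuse cisplatin, and Section 3.2 gives about 100 centers where the protocol synopsis gives about 165. That pattern suggests unreconciled wording, not a deliberate narrowing. Table shells are held in a separate document and may settle the derivation.

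This reading is plausible, and it may be what was meant. But the SAP never points to the combined category, and the protocol lists both terms in every definition, so dropping one changes the rule as written.

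Three further points stand as limits. No hypothesis is tested and no sensitivity analysis is planned, so no inference is at risk. DFS including low-risk recurrence still captures a contralateral recurrence diagnosed by the investigator. Disposition and central DFS can also disagree for other reasons: for example, a central recurrence not diagnosed locally is not communicated to the site. The table mismatch in Step 4 is therefore a weak argument alone.

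**Conclusion.** The concern holds. As written, the SAP's event and censoring rules for centrally reviewed and investigator-reviewed DFS exclude a recurrence type that the protocol counts, and no other SAP category brings it back. This is an error in the rule as stated, not merely missing detail, and should be corrected.

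The effect is confined to descriptive event counts and Kaplan-Meier curves for these two endpoints. Type I error and power are untouched, since nothing is tested. MFS, OS and DFS including low-risk recurrence are unaffected. The number of affected subjects is unknown and may be zero. With few subjects randomized, even one could visibly move a curve.

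The conclusion rests on reading the SAP sentences literally and on the SAP text available, without the separate table shells. If the analysis was in fact programmed from the protocol's combined category, the results would be right and only the wording wrong.

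**What to change.** In SAP Section 4.1 (centrally reviewed and investigator-reviewed DFS) and Section 6 (DFS event and DFS censoring sentences), insert *or contralateral* after local/regional, so that the list matches Protocol Sections 4 and 11.3.3. Add one derivation note saying that the non-metastatic DFS event is taken from the combined invasive category in Protocol 10.1, for the BICR and the investigator data alike. If the narrower event is intended, say so and justify it as a departure from the protocol.

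The same short wording appears in the SAP's description of treatment and follow-up (Section 3.1) and of the long-term follow-up phase (Section 6). Those passages should be reconciled with the protocol at the same time.

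The cost is four edited sentences, one note and the reconciliation. Protocol 10.1 says the recurrence determinations are recorded in the eCRF, so no new data collection should be needed. The protocol does not say where the BICR classification is held, so the programmer should confirm that the central read data can be mapped to the same category.
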